11.2 Assessment of Adverse Events

All AEs and SAEs whether volunteered by the participant, discovered by study personnel during questioning, or detected through physical examination, laboratory test, or other means will be reported appropriately. Each reported AE or SAE will be described by its duration (i.e., start and end dates), regulatory seriousness criteria if applicable, suspected relationship to the study drug (see following guidance), and actions taken. To ensure consistency of AE and SAE causality assessments, only the PI or physician sub-investigators may grade AEs, and investigators should apply the following general guideline:

11.2.1 Relationship to study drug: Yes

There is a plausible temporal relationship between the onset of the AE and administration of the study drug, and the AE cannot be readily explained by the participant's clinical state, intercurrent illness, or concomitant therapies; and/or the AE follows a known pattern of response to the study drug; and/or the AE abates or resolves upon discontinuation of the study drug or dose reduction and, if applicable, reappears upon re-challenge.

11.2.2 Relationship to study drug: No

Evidence exists that the AE has an etiology other than the study drug (e.g., preexisting medical condition, underlying disease, intercurrent illness, or concomitant medication); and/or the AE has no plausible temporal relationship to study drug administration (e.g., cancer diagnosed 2 days after first dose of study drug).

Expected adverse events are those adverse events that are listed or characterized in the Package Insert.

Unexpected adverse events are those not listed in the Package Insert. This includes adverse events for which the specificity or severity is not consistent with the description in the Package Insert. For example, under this definition, hepatic necrosis would be unexpected if the Package Insert only referred to elevated hepatic enzymes or hepatitis.

11.2.3 Diagnosis vs. Signs and Symptoms

If known at the time of reporting, a diagnosis should be reported rather than individual signs and symptoms (e.g., record only liver failure or hepatitis rather than jaundice, asterixis, and elevated transaminases). However, if a constellation of signs and/or symptoms cannot be medically characterized as a single diagnosis or syndrome at the time of reporting, it is ok to report the information that is currently available. If a diagnosis is subsequently established, it should be reported as follow-up information.

11.2.4 Deaths

All deaths that occur during the protocol-specified AE reporting period (see Section 12.1), regardless of attribution, will be reported to the appropriate parties. When recording a death, the event or condition that caused or contributed to the fatal outcome should be reported as the single medical concept. If the cause of death is unknown and cannot be ascertained at the time of reporting, report "Unexplained Death".

11.2.5 Preexisting Medical Conditions

A preexisting medical condition is one that is present at the start of the study. Such conditions should be reported as medical and surgical history. A preexisting medical condition should be re-assessed throughout the trial and reported as an AE or SAE only if the frequency, severity, or character of the condition worsens during the study. When reporting such events, it is important to convey the concept that the preexisting condition has changed by including applicable descriptors (e.g., "more frequent headaches").

11.2.6 Pregnancy

Female Participants

Participants should not become pregnant while on this study and for 90 days after last dose of study drug. In addition, participants should not breastfeed while on this study as these drugs may also affect a breast-feeding child. Pregnant women and women who are breast-feeding are not allowed to participate in this study. Participants must agree to use two medically accepted forms of birth control including condoms, diaphragms, cervical cap, an intra-uterine device (IUD), surgical sterility (tubal ligation or a partner that has undergone a vasectomy), or oral contraceptives, OR must agree to completely abstain from intercourse for at least two weeks before receiving first dose of study drug, during participation in this study and for 90 days after last dose of study drug. Abstinence at certain times of the cycle only, such as during the days of ovulation, after ovulation and withdrawal are not acceptable methods of birth control. Even when an approved contraceptive method is used, there is always a small risk that the participant could still become pregnant.

Male Participants

Participants should not father a child while on this study. If the participants spouse or partner has the potential to become pregnant, the participant and partner must use two medically accepted forms of birth control including condoms, diaphragms, cervical cap, an intra-uterine device (IUD), surgical sterility (vasectomy or a partner that has undergone a tubal ligation), or oral contraceptives, OR must agree to completely abstain from intercourse during participation in this study and for 90 days after last dose of study drug. If the partner is taking oral contraceptives, she must begin taking them at least two weeks before the participants first dose of study drug. Abstinence at certain times of the cycle only, such as during the days of ovulation, after ovulation and withdrawal are not acceptable methods of birth control.

If a female participant becomes pregnant while receiving investigational therapy or within 90 days after the last dose of study drug, the clinical investigator must immediately notify sponsor-investigator (who will then notify Novartis/Sandoz) in accordance with SAE reporting guidelines. Follow-up to obtain the outcome of the pregnancy should also occur. Abortion, whether accidental, therapeutic, or spontaneous, should always be classified as serious, and expeditiously reported as an SAE. Similarly, details of the birth, and the presence or absence of any congenital anomaly/birth defect or maternal and/or newborn complications in a child born to a female participant exposed to the study drug should be reported as an SAE. Follow-up information regarding the course of the pregnancy, including perinatal and neonatal outcome and, where applicable, offspring information must be reported to the sponsor-investigator (and Novartis/ Sandoz). In order for sponsor-investigator or designee to collect any pregnancy surveillance information from the female participant a signed informed consent addendum for disclosure of this information must be obtained (and will be supplied to the IRB for review at the time the incidental pregnancy is encountered, not anticipated and therefore not included with the original protocol documents). Any pregnancy that occurs in a female partner of a male study participant should be reported. Information on this pregnancy will be collected on the Pregnancy Surveillance Form (supplied for IRB review in the event pregnancy in a female partner of a male participant is encountered). In order for sponsor-investigator or designee to collect any pregnancy surveillance information from the female partner, the female partner must sign an informed consent form for disclosure of this information (form to be supplied in the event such a pregnancy were to be encountered).

11.3 UPENN IRB Notification by Investigator-Sponsor

The University of Pennsylvania IRB (Penn IRB) requires expedited reporting of those events related to study participation that are unforeseen and indicate that participants or others are at increased risk of harm. The Penn IRB will not acknowledge safety reports or bulk adverse event submissions that do not meet the criteria outlined below. The Penn IRB requires researchers to submit reports of the following problems within 10 working days from the time the investigator becomes aware of the event:

The PATCH Trial

- Any adverse event (regardless of whether the event is serious or non-serious, on-site or off-site) that occurs any time during or after the research study, which in the opinion of the principal investigator is:

Unexpected (An event is “unexpected” when its specificity and severity are not accurately reflected in the protocol-related documents, such as the IRB-approved research protocol, any applicable investigator brochure, and the current IRB-approved informed consent document and other relevant sources of information, such as product labeling and package inserts.)

AND

Related to the research procedures (An event is “related to the research procedures” if in the opinion of the principal investigator or sponsor, the event was more likely than not to be caused by the research procedures.)

Deaths occurring for patients on-study and within 30 days of study drug administration that are considered unforeseen and indicates participants or others are at increased risk of harm (i.e. unexpected and probably/definitely related), must be reported to the IRB within 24 hours of notification.

See: <https://irb.upenn.edu/> for additional reporting details.

11.3.1 Reporting Process to IRB at Penn.

Principal Investigators are encouraged to submit reports of unanticipated problems posing risks to participants or others using the form: “**Unanticipated Problems Posing Risks to Participants or Others Including Reportable Adverse Events**” via HS-ERA or a written report of the event within 7 working days. FDA Notification by Investigator-Sponsor.

This study is IND exempt and reporting to the FDA is voluntary using a MedWatch 3500 or via the FDA’s website for voluntary reporting.

11.4 Medical Monitoring

It is the responsibility of the Sponsor-Investigator to oversee the safety of the study at this site. This safety monitoring will include careful assessment and appropriate reporting of adverse events, as noted above. Medical monitoring by an independent clinician, [name], Department of Medicine, will include a regular assessment of the number and type of serious adverse events on a periodic basis.

11.7 Study Monitoring Plan

[figure not shown]
This study will be monitored by the Principal Investigator and sub-investigators, as appropriate. Such monitoring will include at least weekly meetings of the study team to review accrual, toxicity, SAEs. Dose escalations and study finding. In addition, the PI will ensure that data are completed in a timely manner and he or his designee will review the data for accuracy, completeness and integrity. Further, the PI will view real-time toxicity and all laboratory results on an ongoing basis by accessing the Monitoring Report database and the Protocol Labs database.

11.8 Auditing and Inspecting

The Investigator is required to permit direct access to the facilities where the study takes place, source documents, CRFs and applicable supporting records of study subject participation for audits and inspections by IRB, regulatory authorities (FDA) and academic authorized representatives (OCR). The Investigator will make every effort to be available for the audits and/or inspections.

12.0 Sample collection and processing for Correlative Science

12.1 Research Specimen Process, Banking and Analysis

Blood and oral fluid specimens collected as delineated in 9.0 Schedule of Events. Samples will be assigned a unique identified and then processed and frozen as per SOP within a BSL2+ space within the Human Immunology Core that is approved by the University of Pennsylvania’s Environmental Health and Radiation Safety (EHRS) program. The processed samples will be stored in the Penn BioBank at the University of Pennsylvania within locked and temperature monitored freezers, and sample tracking will be conducted using the Penn BioBank Laboratory Information Management System (LIMS). Documentation for sample receipt and processing will be collected and stored in either locked cabinet for paper records or within an encrypted and password protected database maintained within the HIC. The planned research analyses outlined in the exploratory objectives will be performed using qualified and if possible validated methods; however, due to nature of these research procedures, they may not conform to principles of good clinical laboratory practice.

13.0 STATISTICAL CONSIDERATIONS

13.1 Sample size calculation

Because we are uncertain about the outcome values for both control and treatment arms of the study, we will use group-sequential methods, initially proposing a real difference that is small, and allowing us to stop early for both efficacy and futility. We conduct two interim analyses and a final analysis, after approximately 1/3, 2/3, and 100% of subjects have completed. We will use the Hwang-Shih-DeCani alpha spending rules. Boundaries for efficacy and futility decisions are show below. Futility boundaries are non-binding.

z-value	Boundaries		Information Proportion
	Efficacy	Futility	
1	2.7819	-0.8235	0.3400
2	2.2653	0.4262	0.6800
3	1.6813	1.6813	1.0000

The PATCH Trial

p-value Stage	Boundaries		Information Proportion
	Efficacy	Futility	
1	0.00270	0.79490	0.3400
2	0.01175	0.33497	0.6800
3	0.04636	0.04636	1.0000

Because we are uncertain about the outcome values for both control and treatment arms of the study, we will use group-sequential methods, initially proposing a real difference that is small, and allowing us to stop early for both efficacy and futility. We conduct two interim analyses and a final analysis, after approximately 1/3, 2/3, and 100% of subjects have completed. We will use the Hwang-Shih-DeCani alpha spending rules. Boundaries for efficacy and futility decisions are show below. Futility boundaries are non-binding.

Sub-Study 1, Home quarantined patients with COVID-19: Given the median duration of viremia is 14-20 days in mild cases, we will assume the null hypothesis that in the placebo cohort the median time to release from quarantine is 10 days from receiving a positive test. In order for HCQ to be considered more effective in this treatment setting we aim to see a median time to release from quarantine of 5 days. These values correspond to daily hazard rates of 0.069 and 0.139 respectively. We will randomize 1:1 HCQ to control and with 100 patients with 50 in the placebo arm and 50 in the HCQ arm. The one-sided z- test ($\alpha=0.05$) will have an overall 95% power to detect a significant difference between the two groups with medians of 10 and 5 days.

The *hypothesis* will be tested using a one-sided test, with a z-score corresponds to the log of the hazard-ratio for recovery between the two groups. We will obtain estimates of the hazard ratio and group median survival, and 95% CI, from Cox regression. As a secondary analysis, we will stratify the analysis, and obtain separate estimates of the hazard-ratio by group. However, we are not powered to test the interaction for significance, and we do not expect significance within group.

Interim analysis: We will perform two interim analyses targeting 34% and 68% completion, testing for early efficacy or futility, using z-score boundaries that follow Hwang-Shih-DeCani alpha spending rules. The determination of information for survival analysis is somewhat imprecise during the planning stages; for that reason, we will conduct analyses when 34% and 68% of the final sample have had 10 days of followup, and determine boundaries based on actual information available at analysis time. Following those rules, we have 95% power using 100% of the sample, if our under our 5 days versus 10 days scenario is true. Under those circumstances, we expect to have a 18% chance of stopping for early efficacy at the first interim analysis. We also have a 30% chance of stopping early for efficacy at the first interim analysis if the placebo arm really had 12 days median time instead of 10 days . Under normal circumstances (10 days v 5 days), we have a 63% chance of stopping for early efficacy at the second interim analysis. We also have an 82% chance of stopping early for efficacy at the second interim analysis if the placebo arm really has 12 days median time instead of 10

Z-Value Boundaries

Maximum Information: 2000.1128

Alternative Hypothesis: $h_1 - h_2 < 0$ (one-sided)

Futility Boundaries: Non-Binding

Stage	Boundaries		Time Proportion	Time	Information Proportion
	Efficacy	Futility			
1	-2.7370	0.7159	0.4000	24.00	0.3660
2	-2.2814	-0.3990	0.6300	37.80	0.6740
3	-1.6808	-1.6808	1.0000	60.00	1.0000

P-Value Boundaries

Maximum Information: 2000.1128

Alternative Hypothesis: $h_1 - h_2 < 0$ (one-sided)

Futility Boundaries: Non-Binding

P-value boundaries are one-sided values.

Stage	Boundaries		Time	Time	Information
	Efficacy	Futility	Proportion	Time	Proportion
1	0.00310	0.76297	0.4000	24.00	0.3660
2	0.01126	0.34494	0.6300	37.80	0.6740
3	0.04640	0.04640	1.0000	60.00	1.0000

Sub-Study 2, Hospitalized patients: We will assume the null hypothesis that in the low dose HCQ cohort 70% of hospitalized patients recover by 21 days. In order for high dose HCQ to be considered more effective in the treatment setting we aim to see a 95% recovery (i.e. an effect of at least 25%). We will randomize 1:1 HCQ to control and with 100 patients with 50 in the low dose HCQ arm and 50 in the high dose treatment arm. The one-sided z-test ($\alpha=0.05$) based on the log of the odds-ratio will have 90% power to detect a significant difference between the two groups of greater than 25% between the population rates. The analysis will be stratified by radiographic signs of pneumonia at admission and age.

The *hypothesis* will be tested using a one-sided test, with a z-score corresponds to the log of the odds-ratio for recovery between the two groups. We will obtain the estimate of the odds ratio, and 95% CI, from logistic regression. As a secondary analysis, we will stratify the analysis, and obtain separate estimates of the odds-ratio by group. However, we are not powered to test the interaction for significance, and we do not expect significance within group.

Interim analysis: We will perform two interim analyses at 34% and 68% completion, testing for early efficacy or futility, using z-score boundaries that follow Hwang-Shih-DeCani alpha spending rules. Following those rules, we have 95% power using 100% of the sample, if our under our 70% versus 95% scenario is true. Under those circumstances, we have a 17% chance of stopping for early efficacy at the first interim analysis. We also have a 92% chance of stopping early for efficacy at the first interim analysis if the low dose arm really has 30% recovery instead of 70%. Under normal circumstances (70% v 95%), we have a 67% chance of stopping for early efficacy at the second interim analysis. We also have a 90% chance of stopping early for efficacy at the second interim analysis if the low dose arm really has 60% recovery instead of 70%.

Stage	Boundaries		Information
	Efficacy	Futility	Proportion
1	2.7819	-0.8235	0.3400
2	2.2653	0.4262	0.6800
3	1.6813	1.6813	1.0000

Stage	Boundaries		Information
	Efficacy	Futility	Proportion
1	0.00270	0.79490	0.3400
2	0.01175	0.33497	0.6800
3	0.04636	0.04636	1.0000

Sub-Study 3, prophylaxis in hospital workers: The transmission of SARS-COV2 from patient to hospital worker depends on many factors including specifics of standard care to prevent transmission, but especially on the number of patients seen at a given hospital or outpatient practice. Across China the reported hospital worker infection rate is 3.8%, but in Wuhan it is reported as 58% at the height of the epidemic. We will use a

10% transmission rate as the null hypothesis (low dose group). In order for HCQ to be considered effective our alternative hypothesis will be a 1% transmission rate. With a 1:1 randomization for the HCQ to control arms we would require a total of 200 hospital worker subjects total for Arm 4. With the placebo group of 100 subjects and the h HCQ arm of 100 subjects, a one-sided z-test ($\alpha=0.05$) comparing the rates in the two groups would have an 80% power to detect a significant difference when the difference in the population rates is at least 9%.

The *hypothesis* will be tested using a one-sided test, with a z-score corresponds to the log of the odds-ratio for recovery between the two groups. We will obtain the estimate of the odds ratio, and 95% CI, from logistic regression.

Interim analysis: We will perform two interim analyses at 25% and 50% completion, testing for early efficacy or futility, using z-score boundaries that follow Hwang-Shih-DeCani alpha spending rules. Following those rules, we have 84% power using 100% of the sample, if our under our 10% versus 1% scenario is true. Under those circumstances, we have a 6% chance of stopping for early efficacy at the first interim analysis. We also have an 81% chance of stopping early for efficacy at the first interim analysis if the low dose arm really has 45% infection instead of 10%. Under normal circumstances (10% v 1%), we have a 27% chance of stopping for early efficacy at the second interim analysis. We also have an 80% chance of stopping early for efficacy at the second interim analysis if the low dose arm really has 23% infection instead of 10%.

Z-Value Boundaries

Stage	Boundaries		Information
	Efficacy	Futility	Proportion
1	2.9473	-1.2318	0.2500
2	2.5825	-0.2676	0.5000
3	1.6664	1.6664	1.0000

P-Value Boundaries

Stage	Boundaries		Information
	Efficacy	Futility	Proportion
1	0.00160	0.89099	0.2500
2	0.00491	0.60550	0.5000
3	0.04782	0.04782	1.0000

12.2 Analysis of Secondary Endpoints.

Secondary outcomes will at least be analyzed as summary statistics, with group means, odds-ratios, and 95% CIs. We may conduct exploratory analyses using regression methods appropriate for each type of measure.

Sub-Study 1: Rate of secondary infection of housemates is a binomial count by household. We will summarize the proportion or rate by group, with 95% CI. With sufficient data, we will explore subgroups, patient, and secondary patient characteristics using logistic regression. Rate of hospitalization is a binary measure. We will summarize rates by group, and estimate the odds-ratio for treatment. Adverse event rates will be summarized as a count by subject, and mean count by group, and we will estimate a rate-ratio for treatment.

Sub-Study 2: The rate of ICU admission is a binary variable by subject. We will summarize the rates by group, and calculate an odds-ratio for treatment. Time to PCR negativity is a time to event measure, beginning at diagnosis time and ending at negativity or censorship. Time to negativity will be summarized using Kaplan-Meier methods to give time-to-event curves by group, and estimates of median time. We will

also estimate a hazard ratio by group. Adverse event rates will be summarized as a count by subject, and mean count by group, and we will estimate a rate-ratio for treatment.

Sub-Study 3: For hospital employees, we will summarize the count of shifts missed by group, and estimate the rate ratio for treatment. Adverse event rates will be summarized as a count by subject, and mean count by group, and we will estimate a rate-ratio for treatment.

REFERENCES

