2.0 OBJECTIVES

2.1 PRIMARY OBJECTIVES

Sub-Study 1 (home quarantined COVID-19 patients): Median time to release from quarantine by meeting the following criteria: 1) No fever for 72 hours without the use of fever-reducing medication 2) improvement in other symptoms and 3) 7 or 10 days have elapsed since the beginning of symptom onset, depending on CDC guidelines at the time. (Outcomes based on 7 and 10 days will be constructed for each subject.)

The first date of quarantine will be considered the date of SARS-CoV-2 nasopharyngeal swab test that confirmed positivity.

Sub-Study 3 Healthcare worker prophylaxis: Rate of COVID-19 infection at 2 months

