2.4 Low dose versus high dose HCQ. In HCQ studies in cancer patients we conducted population pharmacokinetic studies and pharmacodynamic studies and determined that 800-1200 mg daily was required to effectively and consistently impair the lysosome in peripheral blood mononuclear cells. Our PK studies determined that it took roughly 2 weeks to achieve steady state in cancer patients. For these reasons there is rationale to propose a high dose (600 mg po bid) prolonged schedule treatment (2 weeks). In contrast an in vitro study recently published which included PK-PD modeling extrapolated from published PK studies indicated that HCQ was very active against COVID-19 but only 400 mg po bid X1 followed by 200 mg po bid for 5-10 days was enough for treatment. A recent non-randomized open label French trial (Gautret et al Int. J Antimicrobial Agents 2020) showed that 600 mg qd of HCQ cleared virus in 70 % of mildly ill hospitalized patients compared to 12.5% at 6 days of control patients. This generates a major question in how to use this agent in different populations that can best be answered in this three-part placebo controlled randomized trial.

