Given the median duration of viremia is 14-20 days in mild cases, we will assume the null hypothesis that in the placebo cohort the median time to release from quarantine is 10 days from receiving a positive test. In order for HCQ to be considered more effective in this treatment setting we aim to see a median time to release from quarantine of 5 days. These values correspond to daily hazard rates of 0.069 and 0.139 respectively. We will randomize 1:1 HCQ to control and with 100 patients with 50 in the placebo arm and 50 in the HCQ arm. The one-sided z- test (alpha=.05) will have an overall 95% power to detect a significant difference between the two groups with medians of 10 and 5 days.

Based on the new CDC guidelines for quarantine release we will modify the analysis as follows: Given the median duration of viremia is 14-28 days in mild cases, we will assume the null hypothesis that in the placebo cohort the median time to release from quarantine is 14 days from receiving a positive test. In order for HCQ to be considered more effective in this treatment setting we aim to see a median time to release from quarantine of 7 days. These values correspond to daily hazard rates of 0.048 and 0.094 respectively. We will randomize 1:1 HCQ to control and with 100 patients with 50 in the placebo arm and 50 in the HCQ arm. The one-sided z- test (alpha=.05) will have an overall 93% power to detect a significant difference between the two groups with medians of 14 and 7 days.

The *hypothesis* will be tested using a one-sided test, with a z-score corresponds to the log of the hazard-ratio for recovery between the two groups. We will obtain estimates of the hazard ratio and group median survival, and 95% CI, from Cox regression. As a secondary analysis, we will stratify the analysis, and obtain separate estimates of the hazard-ratio by group. However, we are not powered to test the interaction for significance, and we do not expect significance within group.

Given that 20 subjects were recruited and treated under the old CDC guidance, we will conduct a primary analysis based on the updated 10-days from onset criterion. For the subjects who were released under the old criterion, this number will be constructed by assessing when a patient would have been released under the new rules. We will follow that with additional secondary analyses to assess the sensitivity of the results to the change in

The PATCH Trial

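### Sub-Study 1: the arm medians that define the primary objective, and their confidence intervals, come only from a proportional-hazards Cox fit, with no Kaplan-Meier estimate or check of the assumption

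*Protocol*

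**What the plan says.** Section 2.1 of the current protocol states the primary objective as "Sub-Study 1 (home quarantined COVID-19 patients): Median time to release from quarantine by meeting the following criteria". Section 13.1 tests the hypothesis one-sided, "with a z-score corresponds to the log of the hazard-ratio for recovery between the two groups", and then says "We will obtain estimates of the hazard ratio and group median survival, and 95% CI, from Cox regression". The sentence is the same in the original protocol, so the amendments left it alone.

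Planning in Section 13.1 uses one constant daily hazard per arm, which is a proportional-hazards model. For the current 14-day and 7-day medians the plan "will have an overall 93% power to detect a significant difference between the two groups with medians of 14 and 7 days".

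For Sub-Study 1 the current protocol plans no Kaplan-Meier median, no check of proportional hazards and no fallback. The SAP covers Sub-Study 3 only, so it adds nothing here.

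**The concern.** A Cox model that yields a treatment hazard ratio has one treatment term. The two arms then share a baseline cumulative hazard and differ by a constant multiplier. Each arm's median therefore depends partly on the other arm's data, and is right only if the multiplier really is constant.

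The protocol contains three reasons to doubt that:

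- Section 2.4: "Our PK studies determined that it took roughly 2 weeks to achieve steady state in cancer patients", which points to an effect that builds up.
- Section 7.4: treatment ends by two weeks, or earlier at release.
- Section 7.5: placebo participants whose symptoms progress after at least 7 days may cross over to HCQ.

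At stake is the reported primary quantity, days of quarantine saved, and its interval. A late effect would be overstated and an early one understated. The Cox-based interval would not reflect the error, because it assumes the model is correct.

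**Working it through.** **1. The plan's own figures.** With 1:1 allocation and d events, power ≈ Φ(√(d/4)·ln HR − 1.645), and HR = 2 in both scenarios (10 v 5 and 14 v 7 days).

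- d = 100: 5 × 0.693 − 1.645 = 1.82, power 96.6% (96.4% with the printed efficacy boundaries).
- d = 90: 4.743 × 0.693 − 1.645 = 1.64, power 95.0%. The stated 95% for 10 v 5 days reproduces with 90 to 95 events.
- d = 85: 4.610 × 0.693 − 1.645 = 1.55, power 93.9% (93.7% with the boundaries). The stated 93% for 14 v 7 days is consistent with about 85 events. That count assumes 50 days of accrual within 60.

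These figures concern the log hazard ratio test. They do not depend on how the medians are estimated.

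**2. How the medians arise.** The Cox median in arm x (0 placebo, 1 HCQ) is the time t at which H0(t)·exp(bx) = ln 2, with a single H0 and a single b for both arms. The Kaplan-Meier median uses that arm's data alone.

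**3. Under the planning model.** With exponential arms (14 v 7 and 10 v 5 days), the large-sample Cox bias per arm is within 0.1 day. A release floor common to both arms, with proportional hazards after it, also leaves the bias within 0.1 day, so the quarantine rule alone does not break the model.

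**4. Direction of error when the ratio changes.** Placebo is exponential with median 14 days, with no release floor and censoring at day 28 or 60 (the alternative curves and the censoring are assumptions). Example of a true value: no effect for 7 days, then HR 2.5. Half the cumulative hazard to the median is used by day 7 and the rest takes 7/2.5 = 2.8 days. The HCQ median is 9.8 and the true difference 14 − 9.8 = 4.2 days.

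| Assumed pattern | True difference (days) | Cox-based difference |
|---|---|---|
| Constant HR 2 | 7.0 | 7.0 to 7.05 |
| None to day 7, then HR 2.5 | 4.2 | 5.1 to 5.5 |
| HR 2 to day 14, then 1 | 7.0 | 4.7 to 5.3 |
| None to day 14, then HR 2 | 0 | 3.1 to 3.7 |

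The large-sample Kaplan-Meier bias stays within 0.15 day in every pattern examined.

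**5. Restricting to what the protocol allows.** Time zero is the date of the positive swab (Section 2.1). Symptoms began at most 4 days before testing (Section 3.1.3). The primary analysis requires 10 days from onset (Sections 10.2 and 13.1). The earliest release is therefore 10 − 4 = day 6, and the table, which lets releases start at day 0, overstates the sizes. With a day-6 floor and a placebo median of 14 days, the bias in the difference of medians is:

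- modest late effect or partial crossover: about 0.4 to 0.7 day;
- effect that vanishes at day 14: about 1.0 to 1.4 days;
- strong patterns overall: about 1 to 2.2 days, with an effect absent until day 14 near the top.

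Against the 7-day target difference, 0.4 to 0.7 day is 6 to 10%, and 1 to 2.2 days is 14 to 31%.

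**6. Price of Kaplan-Meier at 50 per arm, hazards proportional (14 v 7).** The SD of the median is 2.88 v 2.70 days for placebo (ratio 1.07) and 1.42 v 1.28 for HCQ (ratio 1.11), Kaplan-Meier v Cox. For the difference it is about 3.1 v 2.8 days.

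**The case against.** The case for leaving the text alone has real force. Under the only model the documents state, the Cox medians are unbiased and slightly more precise. In floor-respecting simulations where the ratio changes at day 7, the mean Cox bias was only 0.15 to 0.47 day, and the Cox root-mean-square error was below Kaplan-Meier's (for example 1.59 v 1.71 and 1.93 v 2.32 days with censoring at day 28).

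The mechanisms are also softer than they look. Section 4.1.1 notes that the drug's half-life is many days, so an effect would not stop abruptly at day 14. Crossover is optional and limited to participants who progress without being hospitalised. Success and stopping rest on the log hazard ratio, and nothing forbids reporting Kaplan-Meier curves as well. All of this stands. It limits the size of the point but does not supply the missing check.

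In the strong patterns the precision advantage no longer rescues the Cox estimate. Without the floor, with no effect for 14 days and then HR 2, the root-mean-square error in the HCQ arm was 2.54 days for Cox and 2.18 for Kaplan-Meier.

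Three stronger readings are tempting, and the documents do not support them:

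- *That the planned medians will be off by 1 to 2.5 days.* The documents specify no departure from proportional hazards. The largest such figures come from curves with releases before day 6, which the quarantine rule excludes.
- *That Kaplan-Meier medians would be accurate.* They avoid this bias but remain variable at 50 per arm.
- *That the protocol treats two time-to-event outcomes inconsistently.* The sentence "Time to negativity will be summarized using Kaplan-Meier methods to give time-to-event curves by group, and estimates of median time" belongs to a secondary outcome of Sub-Study 2 in the original protocol. That sub-study was closed, and the current section on secondary endpoints has no such text.

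**Conclusion.** The point holds as a weakness in how the primary quantity is estimated. It is not a flaw in the test. The medians and their intervals rest wholly on an assumption that the protocol gives some reason to question and does not plan to check.

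The bias is nil if hazards are proportional. It is roughly 0.4 to 0.7 day in the difference for modest departures and 1 to 2.2 days for strong ones. These ranges assume a day-6 floor, a placebo median of 14 days and time patterns chosen for illustration. Even the upper figure is smaller than the sampling SD of the difference in the planned exponential case (about 3 days).

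A reader might infer that type I error or the stated power is compromised. It is not: both attach to the log hazard ratio, and under the null the hazards are equal and so proportional. The change is worth making because it is cheap. It is an improvement rather than a condition for the trial's validity.

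**What to change.** Replace the estimation sentence for Sub-Study 1 in Section 13.1 of the current protocol with:

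> Median time to release and its 95% CI will be estimated in each arm by Kaplan-Meier; the hazard ratio and the primary one-sided z will come from Cox regression, with a check of proportional hazards.

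The introduction to the protocol supplement says Sub-Study 1 is still enrolling and will be reported separately, so on the documents' account there was still time to make the change.

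The cost is one sentence, plus up to about 10% loss of precision in the medians if hazards are proportional. Kaplan-Meier medians remain noisy at 50 per arm (SD about 2.9 and 1.4 days in the planned 14 v 7 case), so the intervals should be reported with them. The primary test, boundaries, power and sample size stay as they are.
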